17.1.6. Dose Limiting Toxicity (DLT)

A detailed definition of DLT can be found in Protocol Section 4.1.2. On the CRF, DLT will be identified among all AEs using question “Is it DLT?”, and details will be captured on CRF page “DLT Assessment”. Incidence of DLTs by SOC and PT will be summarized for DLT set. Time between date of first dose of study medication and DLT event onset will be presented for DLT evaluable set.

All relevant information of DLT assessment will be listed for DLT evaluable set by dose cohort and by patient.

17.1.7. Deaths

If any patients die during the study conduct, as recorded on the “Death” CRF form, the count and cause of death and on treatment death (event occurs on or after first study medication dose and prior to 37 days [30 days + 7 days window] after the last dose) will be summarized by dose level in dose escalation phase, and by disease cohort in dose expansion phase.

Individual information of subject ID, death date and primary reason for death will be presented in the listing. On-treatment death will be flagged.

17.2. LABORATORY EVALUATIONS

Laboratory samples will be analyzed at the study site’s local laboratory. Laboratory assessments will include the following:

- Hematology, which is recorded on CRF page “LAB – Hematology”
- Coagulation, INR and aPTT, which is captured on CRF page “LAB - Coagulation”.

- Serum chemistry, which is recorded on CRF page “LAB - Blood Chemistry”
- Serum pregnancy test at screening for all women of childbearing potential, which is captured on CRF page “Pregnancy Test”
- Urinalysis, which is recorded on CRF page “LAB – Urinalysis” and “LAB- 24hrs Urine Protein”
- Thyroid function: TSH, free T3, free T4, which is captured on CRF page “LAB - Thyroid Function Tests”
- Stool occult blood test, which is recorded on CRF page “LAB - Fecal Occult Blood Test”

Test normal ranges of all quantitative tests above (ie, all tests excluding stool occult blood test and serum pregnancy test) are also recorded on corresponding normal range CRF pages.

Data recorded by the laboratory will be converted to the International System of Units (SI) and all presentations will use SI units. Quantitative laboratory measurements reported as “ $< X$ ”, i.e. below the lower limit of normal range (LLN), or “ $> X$ ”, i.e. above the upper limit of normal range (ULN), will be converted to X for the purpose of quantitative summaries, but will be presented as recorded, i.e. as “ $< X$ ” or “ $> X$ ” in the listings.

The following summaries will be provided for laboratory data:

- For quantitative results, actual value of each scheduled visit, change from baseline for each post-baseline scheduled measurement.
- For quantitative measurements and categorical measurements, Incidence of abnormal values assessed by investigator. Shift from baseline according to markedly abnormal criteria based on investigators' assessment.
- Shift from baseline to worst grade in CTCAE grade according to Common Toxicity (CTC) grading system for parameters of hematology and serum biochemistry whose CTCAE scale is available.
- Listing of all laboratory data by patient, abnormal values identified according to normal range (low, normal and high), and markedly abnormal criteria by investigators' assessment will be flagged.

17.2.1. Laboratory Specific Derivations

Creatinine clearance (CCr) will be calculated by using the serum creatinine (SCr) values according to the following formulas:

[figure not shown]
- Male: $CCr = [(140 - \text{age}) \times \text{weight (kg)}] / [0.818 \times SCr (\mu\text{mol/L})]$
- Female: $CCr = [(140 - \text{age}) \times \text{weight (kg)}] / [0.818 \times SCr (\mu\text{mol/L})] \times 0.85$

The units for creatinine clearance will be converted to SI unit: $\mu\text{mol/L}$.

17.2.2. Laboratory Reference Ranges and Markedly Abnormal Criteria

All laboratory assessments except serum pregnancy test and stool occult blood test will be analyzed as following. Quantitative laboratory measurements will be compared with the relevant laboratory reference ranges in SI units and

CCI

categorized as:

- Low: Below the lower limit of the laboratory reference range.
- Normal: Within the laboratory reference range (upper and lower limit included).
- High: Above the upper limit of the laboratory reference range.

In addition to the high and low quantitative laboratory assignments (as identified by means of the laboratory reference ranges), markedly abnormal quantitative safety (and other) laboratory assessments will also be evaluated as normal/abnormal, not clinically significant (NCS)/ abnormal, clinically significant (CS) by investigator. For laboratory assessments collected with both quantitative and qualitative results, if most assessments are quantitative, quantitative assessments will be summarized, and vice versa if most assessments are qualitative, and all the assessments will be listed.

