Section 16 - Appendices (section added) Appendix 1 Study Flowcharts (formerly Appendix A) Appendix 2 ECOG Performance Status (formerly Appendix B) Appendix 3 Response Evaluation Criteria in Solid Tumors Version 1.1 (formerly Appendix C) Appendix 4 Guidelines for Interaction between Surufatinib and Concomitant Medication (formerly Appendix D) Appendix 5 Guideline to Interpreting the Causality Question (formerly Appendix E) Appendix 6 Prohibited Concomitant Medications That Have a Known Risk of QT Prolongation and/or Torsades DES Pointes (TDP) (formerly Appendix F) Appendix 7 Clinical Evaluation of Possible Drug-Induced Liver Injury (DILI) (formerly Appendix G) Appendix 8 Conversion of Urinalysis Results Table (formerly Appendix H)	Added level 1 section for appendices. Revised appendix numbering Align with sponsor's clinical study protocol template	

Protocol Amendment 10 (Version 6.0, 28 Feb 2020)

Amendment Rationale

The primary objective of this amendment is to include a section to highlight the benefit and risk assessment of surufatinib, allow the inclusion of Synovial Sarcoma patients, and to update the Investigator Brochure version referenced, along with supporting data.

Section Number	Description of Changes
2.3 Benefit and Risk Assessment (new section)	Section added as it was not included in previous version.
5.1 Inclusion Criteria	Addition of Synovial Sarcoma subtype in the STS arm (Arm D), along with applicable language throughout protocol.
4.2 Sample Size	Addition of 10 patients to Arm D
3 Study Objectives and Endpoints	Reorganized such that all endpoint subcategories (ie, safety endpoint, efficacy endpoint, pharmacokinetic endpoint) are grouped together under secondary endpoints. This is to comply with endpoint categories defined in clinical trial registries.
6.1.7 Important Safety Risks Table 5	Table and risk language updated to align with current version of surufatinib Investigator Brochure (v9).
6.1.4	Clarified that room temperature for drug storage is between 10°C to 30°C protected from light and moisture.
9 Statistical Analysis	Added that final analysis for each cohort will occur once the last patient had been followed for sufficient time for the analysis of primary endpoint.
Appendix H new section	Inclusion of a urinalysis conversion table for reference
Throughout the document	Editorial revisions were made for clarity and consistency.

Protocol Amendment 9 (Version 5.1, 27 Sep 2019)

Amendment Rationale

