Table 10	Dose Modification for Hemorrhage.....	63
Table 11	Pharmacokinetic Sampling Time Points	70
Table 12	Schedule of Events.....	95

LIST OF APPENDICES

Appendix 1	Study Flowcharts	95
Appendix 2	ECOG Performance Status	99
Appendix 3	Response Evaluation Criteria in Solid Tumors Version 1.1	100
Appendix 4	Guidelines for Interaction between Surufatinib and Concomitant Medication .	111
Appendix 5	Guideline to Interpreting the Causality Question	114
Appendix 6	Prohibited Concomitant Medications That Have a Known Risk of QT Prolongation and/or Torsades DES Pointes (TDP).....	115
Appendix 7	Clinical Evaluation of Possible Drug-Induced Liver Injury (DILI)	117
Appendix 8	Conversion of Urinalysis Results Table	119

LIST OF ABBREVIATIONS

Abbreviations	Definition
AE	Adverse event
ALT	Alanine amino transaminase
ANC	Absolute neutrophil count
AST	Aspartate aminotransaminase
BRCP	Breast cancer receptor protein
BTC	Biliary tract cancer
CA 19-9	Carbohydrate antigen 19-9
CEA	Carcinoembryonic antigen
CFR	Code of Federal Regulations
CgA	Chromogranin A
CI	Confidence interval
CL/F	Apparent clearance
C _{max}	Maximum concentration
CR	Complete response
CRF	Case report form
CRO	Contract research organization
CSF1R	Colony stimulating factor 1 receptor
CT	Computed tomography
CTC	Common toxicity criteria
CTC AE	Common terminology criteria for adverse events
DCR	Disease control rate
DILI	Drug-induced liver inquiry
DLT	Dose-limiting toxicity
DoR	Duration of response
DVT	Deep vein thrombosis
EAS	Efficacy analysis set
ECG	Electrocardiogram
ECOG	Eastern Cooperative Oncology Group
eCRF	Electronic case report form
EDC	Electronic data capture
EGFR	Epidermal growth factor receptor
EC	Ethics Committee
epNET	Extrapancreatic neuroendocrine tumor
FGFR1	Fibroblast growth factor receptor 1

Abbreviations	Definition
G1	Grade 1 (refers to BTC, pNETs, and epNETs)
G2	Grade 2 (refers to BTC, pNETs, and epNETs)
GCP	Good Clinical Practice
GI	Gastrointestinal
HIV	Human immunodeficiency virus
HR	Hazard ratio
HUVEC(s)	Human umbilical vein epithelial cells
IB	Investigator's Brochure
ICF	Informed consent form
ICH	International Conference on Harmonisation
IHC	Immunohistochemistry
INN	International nonproprietary name
INR	International normalized ratio
IRB	Institutional Review Board
IUD	Intrauterine device
IUS	Intrauterine hormone-releasing system
KDR	Kinase domain insert receptor

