8.1.3 Laboratory Test Evaluations

Samples for hematology, serum chemistry, urinalysis and pregnancy testing will be analyzed at the study site's local laboratory. Laboratory assessments will include the following:

Hematology: complete blood count [CBC], including red blood cell [RBC] count, hemoglobin, hematocrit, white blood cell [WBC] count with differential [neutrophils, eosinophils, lymphocytes, monocytes, basophils, and other cells], and platelet count), INR, PT and aPTT.

Serum chemistry: blood urea nitrogen [BUN], creatinine, sodium, potassium, chloride, bicarbonate, calcium, magnesium, phosphate, glucose, total bilirubin, direct bilirubin, ALT, AST, alkaline phosphatase, lactic dehydrogenase [LDH], amylase, total cholesterol, triglycerides, total protein, albumin, and uric acid.

Serum pregnancy test at screening and within 30 days after treatment completion for all women of childbearing potential, including those who have had a tubal ligation. In

addition, urine pregnancy tests will be performed on Day 1 of Cycle 2, and continue on Day 1 at each 28-day cycle thereafter.

Urinalysis (pH, glucose, protein, and blood); if there is $\geq 2+$ protein on urinalysis, then a 24-hour urine protein should be done within in one week. For urinalysis results conversions, please refer to Appendix H

Thyroid function: TSH, free T3, free T4 ;

Stool blood test (as per the institutions standard practice);

Plasma surufatinib concentrations (for PK evaluations) will be assessed using a validated assay.

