9. OUTPUT PRESENTATIONS

Appendix 1 details the conventions for presentation of data in outputs.

The templates provided with this SAP describe the presentations for this study and therefore the format and content of the summary tables, figures and listings to be provided by IQVIA Biostatistics.

Continuous variables will be summarized using descriptive statistics, i.e., number of patients(n), mean, median, standard deviation (SD), and ranges (minimum, maximum).

Qualitative variables will be summarized by count(s) and percentages (%). Unless otherwise stated, the calculation of percentages will be based on the total number of included in the relevant analysis set.

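### SAP 17.2.2 summarises only the majority format of a mixed-format laboratory test and does not use the protocol's urinalysis conversion table, so some urine protein results could be listed but not summarised

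*SAP*

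**What the plan says.** **The rule.** SAP 17.2.2 covers all laboratory assessments except the serum pregnancy and stool blood tests. For a test with results in both formats, it says: "if most assessments are quantitative, quantitative assessments will be summarized, and vice versa if most assessments are qualitative". The sentence ends "and all the assessments will be listed", so nothing is deleted. What the minority format loses is its place in the summaries.

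**The planned summaries.** SAP 17.2 lists four outputs:
- values and change from baseline, for quantitative results;
- investigator-assessed abnormality and the shift based on it, introduced as covering quantitative and categorical measurements;
- CTCAE shifts, for hematology and serum biochemistry;
- listings.

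SAP 17.2.2 adds a low/normal/high classification of quantitative values. SAP 9 sets a default for percentages: unless stated otherwise, "the calculation of percentages will be based on the total number of included in the relevant analysis set".

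**The conversion table.** Protocol 8.1.3 has urinalysis done at each site's local laboratory and adds: "For urinalysis results conversions, please refer to Appendix H". In the current List of Appendices that item is Appendix 8, "Conversion of Urinalysis Results Table". The Amendment 10 summary gives its purpose: "Inclusion of a urinalysis conversion table for reference". The SAP does not mention it.

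**The concern.** A mixed-format rule is needed only if mixed formats are expected. Urinalysis is an obvious candidate: it is run locally at about 8 to 15 sites, and the protocol has a conversion table for its results. Where a conversion exists, choosing one format and setting the other aside discards safety data that could have been used.

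Urine protein is where this would matter most. Urinalysis is a named component of the secondary safety endpoint (Protocol 4.2.4). Proteinuria is an identified risk (Protocol 3.3) and has its own dose-modification table (Table 8). In the monotherapy experience described in Protocol 2.3, it is among the related events seen in at least 20% of patients and the Grade 3 or higher events seen in more than 10%. A laboratory table that covers only some patients, without saying so, would give a poor picture of a principal known toxicity.

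**Working it through.** The documents give no figure to reproduce, so the check is mainly a reading of one section against another.

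**Step 1. Which outputs the rule reaches.**

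| Output | Effect on minority-format results |
|---|---|
| Values, change from baseline, low/normal/high (SAP 17.2, 17.2.2) | Left out |
| Investigator-assessed abnormality and shift | Unclear: SAP 17.2 admits both formats, but the majority rule in 17.2.2 directly follows the sentence on investigator assessment, and neither section is given precedence |
| CTCAE shift (SAP 17.2) | Urinalysis not named |
| Listings | Kept |
| Adverse event and special-interest summaries (SAP 17.1) | Rule does not apply |

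The SAP also does not say whether the majority is judged per parameter, visit, cohort or study.

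**Step 2. Whether other outputs replace what is left out.** In part.
- Protocol 9.11 records a laboratory abnormality as an adverse event only if it is clinically significant and needs active management. Lower-grade proteinuria may therefore show only in the laboratory data.
- On treatment, 24-hour urine protein is prompted by a urinalysis result of 2+ or more (Protocol 8.1.3), so it covers a selected subset. It has its own CRF page and is untouched by the rule unless it is pooled with urinalysis protein as one parameter.
- Proteinuria is a special-interest group in SAP Appendix 2, with incidence and time to onset summarised (SAP 17.1.5).
- Listings keep every result but give no rates.

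**Step 3. Possible size, on assumed values.** Let m be the share of patients whose results are in the minority format and p the true incidence of an abnormality. Assume one format per patient, format unrelated to outcome, and a percentage table that keeps the full analysis set as denominator. Then

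reported incidence = p × (1 − m).

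For an assumed p of 40%:
- m = 0 gives 40%;
- m = 10% gives 0.40 × 0.90 = 36%;
- m = 30% gives 0.40 × 0.70 = 28%;
- m = 40% gives 0.40 × 0.60 = 24%;
- m = 49% gives 0.40 × 0.51 = 20.4%.

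If the denominator is instead the patients with a usable result, (1 − m) cancels and the expected value is again p, from fewer patients.

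**Step 4. Whether m must stay below 50%.** The rule counts assessments, not patients. If minority-format patients contribute a assessments each and majority-format patients b each, the rule implies m × a < (1 − m) × b, that is m < b / (a + b). This is 50% only when a = b. If majority-format patients stay on treatment longer, b exceeds a and the patient share can pass 50%.

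**The case against.** The strongest reply is that the harm is conditional and largely covered elsewhere.

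- **No stated split.** The rule is generic and does not name urine protein, and neither document says that sites report it differently. The pointer to the table sits in the laboratory procedures, so sites may already convert results before entry. This stands: the split is an inference.
- **Table contents.** The contents of Appendix 8 are not in the text available for this review, so it cannot be confirmed that the table maps dipstick grades to concentrations in a way that permits pooling. This stands, and it limits the fix to analytes that the table covers.
- **Proteinuria is seen elsewhere.** The CTCAE grade comes from the 24-hour collection (Protocol Table 8, footnote), and the event tables do not use the majority rule. This holds for clinically significant proteinuria, less so for lower grades.

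A reader might go further and infer that whole sites vanish from the proteinuria data, that their missing results count as normal, or that the baseline shift is lost. The documents do not support this. All results are listed. The full-set denominator is only a default, and the output templates are not in the text available here. For CTCAE grading, SAP 17.2.3 keeps missing results as missing. Quantitative summaries carry their own n (SAP 9). SAP 17.2 lists no table of patients at 2+ or more, so the percentages under the working illustrate a mechanism, not a planned output. The shift rests on the investigator's judgement, which need not depend on format, and SAP 17.2 opens that item to both formats.

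**Conclusion.** The point holds as a gap in safety reporting. SAP 17.2.2 sends minority-format results to listings only, and the SAP makes no use of a conversion table that the protocol provides for urinalysis. If formats do differ between local laboratories, those results leave the value, change and reference-range summaries. Whether they also leave the investigator-assessed tables cannot be settled from the text.

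The size is not determinable: it is nil if formats are uniform and grows with the minority share, which is not stated. Understatement of a percentage further requires the default denominator and the assumptions set out in the working. Without that denominator, the cost is lost coverage and precision rather than a lower rate. The event summaries, the 24-hour results and the listings offset part of the loss. The study has no formal hypothesis testing (SAP 7.6), and the primary endpoints and sample size are unaffected.

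**What to change.** In SAP 17.2.2:
1. For urinalysis analytes that Appendix 8 covers, protein in particular and not pH, map results to one ordinal scale before summarising and include both formats. Check the table's contents first.
2. Keep the majority rule only where no conversion exists. State the level at which the majority is judged, use patients with a usable result as the denominator, and report how many results were left out.
3. State that the investigator-assessed abnormality and shift tables include both formats.

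In Protocol 8.1.3, update the pointer from Appendix H to Appendix 8.

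The cost is one mapping step in the laboratory dataset and a few sentences of text, with no new data. The downside is that converted analytes become ordinal and can no longer be summarised by means. The original values can remain in the listings.

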17.2.3. CTCAE Grading for Laboratory Data

Quantitative laboratory measurements will be graded according to NCI CTCAE V4.03 wherever applicable. All grading will be based on lab values (being direct or some derived, corrected values) ONLY, regardless of its interventional or symptomatic consequences.

Some modifications to the grading system will be applied:

- Grade 5 refers to fatal outcomes, which cannot be determined solely by lab values, therefore will not appear in the grading system. In addition to the usual defined categories.
- A further category denoted Grade 0 will include all other laboratory values except missing values.
- Missing results shall be graded as missing.

For some specific parameters with CTCAE grading in both high and low direction (e.g., calcium, glucose, magnesium, potassium, sodium), CTCAE in high and low directions will be presented separately, i.e. hyper for higher values of concern and hypo for lower values of concern.

Shifts in toxicity grade from baseline to the worst toxicity grade will be provided for the SAS.

17.2.4. Liver Function Abnormality

Liver function abnormality is defined in Protocol Section 7.1.7 and the below events will be identified via programming and summarized by categories and dose cohort for SAS. Separate listings for patients with drug-induced liver injury (DILI) will also be provided.

- ALT/AST > 3 x ULN and \leq 5 x ULN
- ALT/AST > 5 x ULN
- Total Bilirubin > 2 x ULN
- ALT/AST > 3 x ULN AND concurrent Total bilirubin > 2 x ULN

CCI

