7.1.7 Important Safety Risks

The important Identified Risks reported for patients who have received surufatinib may be found in the current version of the surufatinib IB.

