	stable or declining, continue with the original dose treatment; If the ALT and/or AST continue to rise significantly, then interrupt surufatinib; resume treatment at a lower dose if transaminase elevation resolves to \leq Grade 1 within 21 days; otherwise discontinue treatment.	
Grade 3: ALT $>5 \times$ ULN or AST $>5 \times$ ULN	Hold surufatinib; resume treatment at the lower dose if resolves to \leq Grade 1 within 21 days; otherwise discontinue treatment.	Check total bilirubin. ^a Provide supportive care and increase the frequency of liver function monitor to twice a week; consult expert if necessary.
Grade 4: ALT $>20 \times$ ULN or AST $>20 \times$ ULN	Discontinue treatment.	Check total bilirubin. ^a Urgent medical intervention indicated.

^a If ALT or AST escalates to 3 times baseline level with bilirubin $>2 \times$ ULN, the biochemical criteria for Hy's Law have been met, surufatinib should be discontinued immediately, and the event should be reported to the sponsor within 24 hours. See [Appendix 7](#) for important additional information.

Table 10 Dose Modification for Hemorrhage

Grade and Definitions	Dose modification	Suggested Actions
Grade 1	None.	Follow up per planned schedule.
Grade 2	Hold surufatinib treatment; Resume at a lower dose if resolves to \leq Grade 1 within 21 days.	Active management.
Grade 3 or higher	Discontinue treatment.	Immediate medical intervention to identify and treat the source of bleeding.

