9.16 Liver Function Abnormality

The finding of an elevated ALT or AST ($>3 \times$ baseline value) in combination with either an elevated total bilirubin ($>2 \times$ ULN) or clinical jaundice in the absence of cholestasis or other causes of hyperbilirubinemia is considered to be an indicator of severe liver injury; these findings meet the definition for Hy’s Law, and are associated with an increased risk of drug-induced liver injury (DILI). Therefore, investigators must report as an AE the occurrence of either of the following:

- Treatment-emergent ALT or AST $>3 \times$ baseline value in combination with total bilirubin $> 2 \times$ ULN (of which 35% is direct bilirubin)
- Treatment-emergent ALT or AST $>3 \times$ baseline value in combination with clinical jaundice

The most appropriate diagnosis or (if a diagnosis cannot be established) the abnormal laboratory values should be recorded on the Adverse Event CRF and reported to the sponsor

or its designee within 1 working day after learning of the event as an SAE. See [Appendix 7](#) for important additional information.

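### SAP 17.2.4 attributes its liver definition to the protocol, but its combined row measures ALT/AST against ULN where the protocol measures against baseline

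*SAP*

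**What the plan says.** SAP 17.2.4 opens: "Liver function abnormality is defined in Protocol Section 7.1.7 and the below events will be identified via programming". It then gives four rows: ALT/AST above 3 and up to 5 × ULN; ALT/AST above 5 × ULN; total bilirubin above 2 × ULN; and the combined row, "ALT/AST > 3 x ULN AND concurrent Total bilirubin > 2 x ULN". Every threshold is a multiple of ULN. The same section adds "Separate listings for patients with drug-induced liver injury (DILI) will also be provided", without stating who enters those listings.

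The protocol section cited is headed "7.1.7 Important Safety Risks" and only points to the Investigator's Brochure. The definition is in Protocol 9.16, where the combined finding "is considered to be an indicator of severe liver injury" and is said to meet Hy's Law. Section 9.16 has two limbs:

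- ALT or AST more than 3 times "baseline value in combination with total bilirubin" above 2 × ULN, with a 35% direct-bilirubin condition;
- ALT or AST more than 3 times "baseline value in combination with clinical jaundice".

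Footnote a to Table 9 (Protocol 7.2.3) uses the same reference for the biochemical Hy's Law criteria: "If ALT or AST escalates to 3 times baseline level with bilirubin" above 2 × ULN. SAP 4.4 declares only additional ECG analyses as changes from the protocol.

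**The concern.** The SAP presents its rows as the protocol's definition, but the transaminase part of the combined row has a different reference point. Two protocol passages agree on baseline; the SAP departs from both without saying so. The wrong section number adds to the doubt. SAP 17.1.1.1 likewise cites Protocol 7.1.5 for CTCAE grading, and that section is Drug Accountability in the protocol version the SAP names. Outdated numbering is therefore a more natural reading than a deliberate choice, although the documents do not settle it.

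At stake is whether the safety tables can show who met the protocol's own criterion. Protocol 3.3 names hepatic disorders as an identified risk. Protocol 2.3 lists raised bilirubin and raised AST among treatment-related events in at least 20% of monotherapy patients, and liver injury and hepatic encephalopathy among the related fatal events. The protocol attaches sponsor reporting and a treatment decision to the baseline-based rule. A ULN-based row cannot be reconciled directly with the events reported under that rule.

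**Working it through.** No sample size or error rate is involved, so the check is a comparison of thresholds.

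Inputs:

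- SAP combined row: ALT/AST above 3 × ULN, with total bilirubin above 2 × ULN (SAP 17.2.4).
- Protocol bilirubin limb: ALT/AST above 3 × baseline, with total bilirubin above 2 × ULN (Protocol 9.16).
- ALT/AST permitted at entry: up to 1.5 × ULN without hepatic metastases, up to 3 × ULN with them (Protocol 6.2, exclusion criterion 4).

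Write baseline ALT or AST as b × ULN. The protocol cut is then 3 × b × ULN and the SAP cut is 3 × ULN. They coincide only when 3b = 3, that is, b = 1. Total bilirubin above 2 × ULN is assumed in every line below; without it neither rule is met.

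| b | Protocol cut (× ULN) | SAP cut (× ULN) | On-study ALT/AST where the rules disagree (× ULN) | SAP combined row |
|---|---|---|---|---|
| 0.5 | 1.5 | 3.0 | above 1.5, up to 3.0 | misses |
| 0.75 | 2.25 | 3.0 | above 2.25, up to 3.0 | misses |
| 1.0 | 3.0 | 3.0 | none | agrees |
| 1.5 | 4.5 | 3.0 | above 3.0, up to 4.5 | flags extra |
| 2.0 | 6.0 | 3.0 | above 3.0, up to 6.0 | flags extra |
| 2.5 | 7.5 | 3.0 | above 3.0, up to 7.5 | flags extra |
| 3.0 | 9.0 | 3.0 | above 3.0, up to 9.0 | flags extra |

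The entry criteria allow every baseline shown; the last three need hepatic metastases.

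Where a missed case still appears: a bilirubin-limb case has total bilirubin above 2 × ULN by definition, so it counts in the SAP's bilirubin row. It is not identified as a combined case. A jaundice-limb case whose bilirubin does not exceed 2 × ULN falls in neither the bilirubin row nor the combined row.

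The two protocol passages differ slightly at the boundary: 9.16 requires more than 3 times baseline, while footnote a speaks of reaching 3 times baseline. That matters only at exact equality and does not change the table.

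**The case against.** The best defence is that the SAP does not label the combined row Hy's Law, that ULN bands match the protocol's own ALT/AST grading in Table 9, and that the study is descriptive with no formal testing. This stands as a reason to keep the ULN rows. Extra flags also do little harm: total bilirubin above 1.5 × ULN is excluded at entry, so a patient flagged above 2 × ULN deserves a look anyway. It does not answer the point that the row is attributed to the protocol and does not apply the protocol's rule.

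A reader might infer more than the documents support:

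- **That cases vanish from the outputs.** Bilirubin-limb cases remain in the bilirubin row. The SAP also provides laboratory listings with changes from baseline, shifts to worst CTCAE grade, and hepatic summaries of events of special interest.
- **That the DILI listing is wrong.** Its selection rule is not stated, so it inherits the mismatch only if it uses the combined row. Protocol Appendix 7, to which both protocol passages refer, is not in the text at hand, and a further criterion there cannot be excluded.
- **That safety reporting is weakened.** Investigators must still report cases under 9.16, and no section gives this table the role of catching cases that sites fail to report.
- **That both kinds of misclassification will occur.** No baseline ALT/AST distribution or rate of hepatic metastases is given. Metastases would bear only on the over-flagging side.
- **That a 20% rise is enough to be flagged.** From b = 2.5, 3.0/2.5 = 1.20, but the combined row also needs bilirubin above 2 × ULN.
- **That Section 7.1.7 once held the definition.** Nothing shows this; it is simply the wrong reference.

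**Conclusion.** The inconsistency is real and confined to the programmed tabulation. The SAP's combined row and the protocol's criterion agree only for a patient whose baseline ALT/AST equals ULN. Below that, the row can miss protocol-defined cases; above it, the row can flag patients who do not meet the protocol rule. The jaundice limb and the direct-bilirubin condition have no counterpart in the SAP, and SAP 4.4 declares none of this.

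The size can be given as threshold windows but not as a patient count. The conclusion rests on 9.16 and footnote a being the operative definitions, and on bilirubin above 2 × ULN in each comparison. It is worth correcting, but it does not touch the efficacy conclusions or the reporting of individual cases. The SAP and protocol passages must be reconciled; no view is taken here on which clinical threshold is right.

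**What to change.** In SAP 17.2.4:

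1. Change the cross-reference from Protocol 7.1.7 to Protocol 9.16.
2. Add a programmed row and a listing flag for treatment-emergent ALT/AST above 3 × baseline with total bilirubin above 2 × ULN, applying the 35% direct-bilirubin condition.
3. Add the clinical-jaundice limb, taking jaundice from the adverse event data.
4. Keep the four ULN-based rows beside the new one.
5. State the selection rule for the DILI listing.

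Record in SAP 4.4 any difference from 9.16 that remains. One candidate is 9.16's qualifier about the absence of cholestasis or another cause of raised bilirubin, which laboratory values alone may not settle.

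The cost is small: a baseline-referenced row, a flag, a link to adverse event terms and a few sentences of text. ALT, AST, total bilirubin and direct bilirubin are already collected (Protocol 8.1.3), and baseline is already defined (SAP 7.2). No new data are needed.
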